1 INTRODUCTION

1.1 Background

With more than 2 million abdominal operations occurring annually in the United States (US), up to 20% of those patients developing ventral incisional hernias, abdominal wall defects and incisional hernias represent a challenging surgical condition.^{1, 2} Approximately 348,000 ventral hernia repairs are performed on a yearly basis.³ There are several options for repair, including primary repair, synthetic or biologic material placement, repair with relaxing incisions, and use of musculofascial flaps, utilizing both open and laparoscopic approaches.² However, there is no clear-cut consensus regarding the optimal hernia repair technique, particularly in complex hernia repair cases where patient co-morbidities exist and a high risk of infection is present.

Simple suture repair has been associated with a high risk of hernia recurrence, with reports ranging from 10% to 55%, and has been nearly abandoned for the repair of hernias which are greater than five centimeters (cm) in size.^{4, 5, 6, 7} Use of synthetic mesh reduces hernia recurrence rates, although its use has been associated with complications such as infection, adhesions, fistulae, and foreign body reactions including increased inflammation and/or connective tissue deposition.⁸

Synthetic mesh repair procedures, either open or laparoscopic, have been reported to lead to fewer recurrences compared to primary repairs.^{9, 10, 11} Improved outcomes are believed to be related to reduced tension on the fascial edges and sutures when mesh is used in hernia repair procedures. However, complex cases and large abdominal wall defects continue to pose a challenge to surgeons. Factors such as patient co-morbidities, defect size, location, tissue viability and degree of contamination are included in a surgeon's assessment and decision-making process.¹² These large abdominal wall defects have been associated with recurrence rates of up to 46%.¹³

Laparoscopic ventral hernia repair was first reported by LeBlanc in 1992, and is popular alternative to open repairs due to the potential benefit of shorter hospital stays, improved patient outcomes, and fewer complications compared to open repairs.^{14, 15} In a large series (850 patients) by Heniford, et al., laparoscopic ventral hernia repair using prosthetic mesh had a low rate of conversion to open surgery (3.4%), length of hospital stay (2.3 days), a moderate complication rate (13.2%), and a low hernia recurrence rate of 4.7% (average follow-up of 20 months).¹⁵ In a study by Orenstein, et al., laparoscopic ventral hernia repair with defect closure had a low recurrence rate (none in 47 consecutive patients out to 16.2 months follow-up).¹⁶ They purported that defect closure eliminated postoperative seromas and patient reports of bulging and reduced the size of implanted mesh.¹⁶

Ideally, a resorbable mesh would provide adequate structural support throughout the healing process and would be fully absorbed when the wound has completely healed, thereby potentially reducing the chances for complications associated with the persistence of non-resorbable mesh material. However, the development of resorbable mesh products has faced

challenges related to the rate of resorption with complications arising when the mesh product is resorbed too quickly. Rapid resorption does not support sufficient healing if structural reinforcement is diminished during the tissue repair period. A resorbable mesh should retain its functional strength for a sufficient period of time to allow native cellular ingrowth tissue remodeling, maturation of collagen, and gradual shift of mechanical load.

Phasix™ Mesh is a commercially available medical device in the US. It is a resorbable mesh prepared from poly-4-hydroxybutyrate (P4HB) which has been studied for use as a biomaterial for a number of applications in medical devices and tissue engineering due to favorable mechanical properties, biocompatibility and desirable degradation times.^{17,18,19} Using standard measures of mechanical strength (suture pull-out, tear and ball burst strength) Phasix™ Mesh is comparable in performance to traditional polypropylene mesh. Pre-clinical implantation studies indicate that the resorption of the Phasix™ Mesh fibers is minimal throughout the 12 week expected period of healing and up to ~26 weeks post-implantation. Resorption of the fibers is essentially complete in 12-18 months.^{21,22} Given the long-term strength retention observed in preclinical studies, it is anticipated that Phasix™ Mesh may result in low recurrence and complication rates with minimal pain and discomfort when used for hernia repair.

A porcine hernia repair study demonstrated that Phasix™ Mesh could perform as a durable scaffold for soft tissue repair.²¹ The results of the 52-week study showed that the repair site had significantly greater mechanical repair strength, as compared to native abdominal wall. Notably, repair strength persisted even after significant Phasix™ Mesh resorption (as measured by molecular weight). Histologically, Phasix™ Mesh showed an initial mild-moderate host inflammatory response, that declined to mild over 52-weeks.

Neovascularization (angiogenesis) and new collagen deposition were evident at 6, 12, 26 and 52-weeks. In a 24-week rat study, histological analyses of the repair site demonstrated that other fully-resorbable competitive meshes had a greater overall host inflammatory response, whereas the response to Phasix™ Mesh was relative comparable to permanent polypropylene mesh.²² In the same study, histological analyses demonstrated similar variability on measures of host fibrotic response.

The subject of this study, Phasix™ ST is a fully resorbable mesh with a hydrogel coating that is also resorbable. It is a sterile mesh device with indication for use in the reinforcement of soft tissue, where weakness exists, in procedures involving soft tissue repair, such as for the repair of hernias. Phasix™ ST Mesh is comprised of a co-knitted mesh and hydrogel coating.

The fascial side of the mesh allows for a prompt fibroblastic response through the interstices of the mesh, allowing for complete tissue ingrowth, similar to P4HB mesh alone. The visceral side of the mesh is coated with a resorbable, chemically modified sodium hyaluronate (HA), carboxymethylcellulose (CMC), and polyethylene glycol (PEG) based hydrogel. The resorbable hydrogel coating functions to separate the mesh from underlying tissues and organ surfaces to help minimize tissue attachment to the mesh. Shortly after hydration in saline, the biopolymer coating becomes a hydrated gel that is resorbed from the site in less than 30-days. See Section 1.3 Device Description, for more information.

A laparoscopic, porcine study was conducted to evaluate peritoneal tissue attachment development 4 weeks after implantation of Phasix™ ST Mesh or Ventralight™ ST Mesh (each group used 4 pigs; 8 meshes). At 4 weeks post-implantation, there were very few instances of light, omental tissue attachments in both groups. The overall tissue attachment scores associated with Phasix™ ST Mesh was not significantly different than for Ventralight™ ST Mesh. These results indicate that the hydrogel barrier (Sepra® Technology) properties associated with Ventralight™ ST Mesh are maintained with Phasix™ ST Mesh.²²

Additional porcine studies were conducted to characterize the strength of a buttress repair over time. Twenty-four, female, Yucatan pigs were implanted bilaterally with mesh according to one of the following: a) underlay repair with Phasix™ ST Mesh; b) underlay repair with Ventralight™ ST Mesh; c) a retromuscular repair with Phasix™ Mesh or d) a retromuscular repair with Strattice™ Firm Reconstructive Matrix. Bilateral surgical defects (1" diameter) were created and subsequently repaired with PDS suture. Mesh devices were placed and fixated with absorbable tacks or sutures. Ball burst strength and host responses were measured at mesh placement and 12- or 24-weeks post-implantation.²²

At 12- or 24-weeks, the burst strength of the Phasix™ ST Mesh repair was at, or slightly above, the burst strength at the time of mesh placement (despite the hydrolysis of the Phasix™ material over these time periods). This suggests a transfer of load from the degrading Phasix™ material to the newly ingrown host tissue. The Strattice™ Firm Reconstructive Matrix repairs showed a significant reduction in strength of the repair site at 12- or 24-weeks and they had significantly lower burst strength relative to Phasix™ and Phasix™ ST Mesh devices. At 12- or 24-weeks, histology demonstrated that a robust and biocompatible ingrowth is associated with the Phasix™ material. Neovascularization occurs more rapidly in the Phasix™ material relative to the Strattice™ Firm Reconstructive Matrix.²²

This post-approval clinical study is being conducted to evaluate the use of Phasix™ ST Mesh in laparoscopic ventral or incisional hernia repair in patients with a higher level of risk for Surgical Site Occurrence (SSO) as defined by the presence of 1 or more comorbid conditions. Patients who receive a Phasix™ ST implant will be followed for 24-months.

1.2 Rationale

This study is intended to evaluate the use of Phasix™ ST for laparoscopic ventral or incisional hernia repair amongst subjects at high risk for SSO.

1.3 Device Descriptions

1.3.1 Phasix™ ST

Phasix™ ST is a fully resorbable mesh with a hydrogel coating that is also resorbable. It is a sterile mesh device with indication for use in the reinforcement of soft tissue, where weakness exists, in procedures involving soft tissue repair, such as for the repair of hernias. Phasix™ ST Mesh is comprised of a co-knitted mesh and hydrogel coating.

Preclinical implantation studies indicate that resorption of the P4HB fibers is minimal throughout the 12 week expected healing period, and remains minimal up to 26-weeks post implantation. Significant degradation of the mesh fibers observed in preclinical studies within 12- to 18-months indicates loss in mechanical integrity and strength of the mesh. While fiber segments were observed at 18-months, they continued to degrade.^{20, 21}

The fascial side of the mesh allows for a prompt fibroblastic response through the interstices of the mesh, allowing for complete tissue ingrowth, similar to P4HB mesh alone. The visceral side of the mesh is coated with a resorbable, chemically modified sodium hyaluronate (HA), carboxymethylcellulose (CMC), and polyethylene glycol (PEG) based hydrogel. The resorbable hydrogel coating functions to separate the mesh from underlying tissues and organ surfaces to help minimize tissue attachment to the mesh. Shortly after hydration in saline, the biopolymer coating becomes a hydrated gel that is resorbed from the site in less than 30-days.

Phasix™ ST Mesh and Phasix™ Mesh are similar in material; with both containing P4HB, the largest percentage of material present in Phasix™ ST Mesh. The difference between the meshes is that Phasix™ Mesh does not have polyglycolic acid (PGA) fibers or a hydrogel coating.

Phasix™ ST Mesh was designed to handle similarly to polypropylene (permanent) mesh at implantation, but it is fully resorbable. It is expected to maintain its strength over the critical healing period; minimize tissue attachment to the mesh, and resorbs, leaving no foreign material behind.

Phasix™ ST is commercially available in the US and indicated for use in the reinforcement of soft tissue, where weakness exists, in procedures involving soft tissue repair, such as for the repair of hernias. Because Phasix™ ST Mesh is fully resorbable, it should not be used in repairs where permanent wound or organ support from the mesh is required. A full description of Phasix™ ST is included in the product's Instructions for Use (IFU).

2 STUDY OBJECTIVES

The objective of this study is to collect additional data on safety, performance and effectiveness of Phasix™ ST in subjects receiving laparoscopic ventral or incisional hernia repair at high risk for SSO. Subjects at high risk are defined as having 1 or more of the following co-morbid conditions: body mass index (BMI) between 30-40 kg/m², inclusive, active smokers, chronic obstructive pulmonary disease (COPD), diabetes, immunosuppression, coronary artery disease, chronic corticosteroid use, low pre-operative

serum albumin, advanced age, or renal insufficiency. The study end points are described below.

3 STUDY ENDPOINTS

There is one primary endpoint, SSO, and eight secondary endpoints:

3.1 Primary Endpoint

1. Surgical Site Occurrence (defined as and of the following complications requiring intervention: surgical site infection (see Appendix 2 for definitions), seroma, hematoma, wound dehiscence, skin necrosis, mesh infection and fistulas) within 45-days post-implantation.

3.2 Secondary Endpoints

1. Surgical Site Occurrence (defined as surgical site infection (see Appendix 2 for definitions), seroma, hematoma, wound dehiscence, skin necrosis, mesh infection and fistulas requiring intervention) > 45-days post-implantation
2. Hernia Recurrence Rate will be assessed by physical examination at each study visit through 24-months. A recurrent hernia will be defined as any hernia identified or confirmed by the investigator, during any study follow-up visit, within 5 cm of the hernia repaired in the study procedure.
3. Surgical Pain Scale - Visual Analog Scale (VAS)
4. Device related adverse event incidence
5. Rate of reoperation due to the index hernia repair
6. Quality of life assessments (Carolinas Comfort Scale® and SF-12®)
7. Surgical procedure time as measured from incision to closure (skin to skin)
8. Length of stay

4 STUDY DESIGN

This is a prospective, multi-center, single-arm, open-label study designed to collect additional data on the safety, performance and effectiveness of Phasix™ ST for laparoscopic ventral or incisional hernia repair. Follow-up visits will be conducted at 1, 3, 6, 12, 18, and 24-months following surgery. See Section 6 for a detailed schedule of study visits and procedures.

5 STUDY POPULATION

5.1 Number of Subjects

This study is projected to treat approximately 120 subjects at approximately 16 US sites.

5.2 Eligibility Criteria

5.2.1 Inclusion Criteria

The subject must meet all of the criteria listed below to be treated in the study:

1. Subject must be 18 years of age or older
2. Subject must be willing to give written informed consent
3. Subject must be diagnosed with ventral or abdominal incisional hernia
4. Subject must be willing to undergo laparoscopic hernia repair using intraabdominal placement (with or without Component Separation Technique (CST))
5. Surgeon must be able to fully close the hernia defect. Defect closure is defined as complete re-approximation of fascial edges, leaving no gap. Since the safety and effectiveness of Phasix™ ST Mesh in bridging repairs has not been evaluated or established, the defect should be closed prior to mesh use.
6. Subject is expected to meet the criteria for a Class I wound as defined by the CDC (Appendix 3)
7. Subjects must have 1 or more of the following pre-study conditions:
 - a. Body Mass Index (BMI) between 30-40 kg/m², inclusive
 - b. Active smoker (including if attempts to quit smoking within two weeks of surgery have failed and the patient is still an active smoker at the time of surgery)
 - c. COPD presence on patient self-report
 - d. Diabetes mellitus (if yes, diagnosis to be confirmed via medical records or laboratory results according to 2014 Joslin Clinical Guideline for Adults with Diabetes)(Appendix 5)
 - e. Immunosuppression
 - f. Coronary Artery Disease
 - g. Chronic corticosteroid use: greater than 6 months systemic use
 - h. Serum albumin less than 3.4 g/dL
 - i. Advanced age: 75 years or older
 - j. Renal insufficiency, defined as serum creatinine concentration ≥ 2.5 mg/dL

5.2.2 Exclusion Criteria

The subject must be excluded from treatment in the study if any of the following criteria are met:

1. Subject has had 4 or more previous hernia repairs (of the index hernia)
2. Subject's hernia is > 350 cm²
3. Complete removal of existing mesh from a prior hernia repair (in the same affected area) is not possible
4. Subject has intact permanent mesh adjacent to the current hernia to be repaired
5. Preperitoneal placement of mesh
6. The subject is known to have a collagen disorder
7. The subject has peritonitis

8. The subject is on or suspected to be placed on chemotherapy medications during any part of the study
9. The subject's Body Mass Index (BMI) is $> 40 \text{ kg/m}^2$
10. The subject has cirrhosis of the liver and/or ascites
11. Subject is American Society of Anesthesiology Class 4 or 5
12. Subject has a life expectancy of less than 2 years at the time of enrollment
13. Subject has any condition that, in the opinion of the Investigator, would preclude the use of the study device, or preclude the subject from completing the follow-up requirements
14. Subject has a surgical wound classified as Class II (Clean-Contaminated), Class III (Contaminated) or Class IV (Dirty-Contaminated) as defined by the CDC (Appendix 3)
15. Subject has an active or latent systemic infection
16. Patient has a contraindication to placement of mesh
17. Subject requires surgical bridge repair as the sole repair
18. Subject is pregnant or has plans to become pregnant during the study period
19. Subject has enrolled in another interventional clinical study within the last 30 days
20. Subject is part of the site personnel directly involved with this study
21. Subject has a known allergy to the test device or component materials (patients with known allergies to tetracycline hydrochloride or kanamycin sulfate should be avoided).

6 STUDY PROCEDURES

6.1 Subject Screening and Baseline Evaluation

Subjects with a diagnosis of ventral or abdominal incisional hernia receiving laparoscopic surgical repair (including robotic-assisted repairs) with defect closure, will be screened for potential eligibility against the study protocol inclusion and exclusion criteria, utilizing ordinary standard of care procedures (e.g., physical examination, blood work, medical evaluation) within 60 days of the date of consent. Since the safety and effectiveness of Phasix™ ST Mesh in bridging repairs has not been evaluated or established, the defect should be closed prior to mesh use. This may include a full anesthetic work-up customary for hernia repair procedures. Any other standard of care examination or evaluation within 60 days of the date of consent may be considered baseline for study purposes. Prior medical records documenting these tests, examinations and evaluations may be used as the source documents for the baseline visit.

During the screening and recruitment process, the Investigator will be responsible for describing the nature of the clinical study, verifying that the eligibility criteria have been met, and obtaining informed consent. Written informed consent and a Health Insurance Portability and Accountability Act (HIPAA) waiver must be obtained prior to performance of any protocol specific procedures.

The following screening/baseline procedures will be conducted and documented.

6.1.1 Informed Consent

The investigator will explain the study to the subject, answer all of the subject's questions, and obtain written informed consent in a language in which the subject is fluent before the collection of any study data or performance of any study procedures.

The subject must be willing and able to sign and date the informed consent form (ICF) prior to the collection of study data or performance of any study procedures. The original, signed informed consent will be retained with the subjects' records and a copy provided to the subject.

6.1.2 Enrollment

Subjects who sign an informed consent will be considered enrolled in this study. Subjects who provide consent for participation but do not meet all of the study eligibility criteria and do not receive the study device will be considered screen failures.

6.1.3 Eligibility

The subject's eligibility for study enrollment will be reviewed and documented on the appropriate eCRF. At the time of screening, a related progress note must be entered in the source documentation to indicate that all eligibility criteria were reviewed and screening results noted. Final eligibility will be determined intraoperatively.

Subjects who fail to meet eligibility criteria should be considered screen failures and treated according to the Investigator's standard of care. Data are to be collected for screen failure subjects from the time the ICF is signed until the subject is deemed a failure. At a minimum, subject demographics and the reason for failure must be collected. Adverse events (AEs) that occur prior to the surgical procedure will be added to the medical history. Any adverse event that occurs from the beginning of the surgical procedure until the subject is determined as screen failure will be recorded on the AE eCRF.

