6.3 Subject Follow-up

6.3.1 Subjects Not Implanted and Surgical Repair Failures

Subjects who are screened but do not have the study device placed should be considered screen failures and treated per hospital standard of care. Screen failure subjects who experience a protocol defined AE will be followed through satisfactory resolution or stabilization of the event.

Reason for failure of the surgical repair procedure, as well as all information outlined in Section 6.2.2 must be recorded in the source documentation.

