9 MECHANICAL FAILURES, MALFUNCTIONS AND DEFECTS

The Investigator will record if a Sponsor device used in the study procedure failed to meet its performance specifications whether due to mechanical failure, malfunction or defects. This applies to: devices used in the subject, devices in which the package was opened but the device was not used for implantation in the subject, or devices with which implantation was attempted, but the device did not remain (was not used) in the subject.

A recurrence (unless it is in a different location than the study hernia) is considered a device failure if the recurrence is considered to be possibly device related, and not procedure related or an issue of patient mismanagement (e.g., mesh used was too small to adequately cover the defect, too much tension, etc.), as determined by the Investigator.

All mechanical failures, malfunctions, missing components, or any other defect of the study device or any components of the device kit that do not perform to specifications must be promptly reported to Davol:

Field Assurance Department
E-mail: [contact]

The event must also be documented on the Device Failure eCRF and the malfunctioning device should be retained for return and evaluation to Davol Field Assurance.

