### **7.9 Adverse Events**

AEs will be collected from the time of enrollment (AE onset after signing ICF) through the end of study participation (either study completion or screen failure or early discontinuation) and will be documented in the medical record or source document and on study eCRFs. All events will be followed to satisfactory resolution or stabilization. AEs that occur prior to the surgical procedure will be added to the medical history. AEs that occur from the time of

surgical procedure will be recorded in the source documentation and on the AE page of the eCRF

AEs will be tabulated by system organ class (SOC) and preferred term (PT) (MedDRA). The total number of events, as well as the number and percentage of subjects with events will be reported. Subjects will also be summarized by severity groups. SAEs will be summarized by SOC and PT.

Subjects with AEs related to the procedure (definitely or possibly related; in case of a missing classification of the relationship to procedure a relation to the procedure is assumed) will be summarized with frequency and percentage. Device related AEs will be summarized similarly.

Subjects who do not have PhasixTM ST implanted will have their AEs summarized separately and their outcome data will not be collected or analyzed.

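### Subjects in whom the mesh was tried but did not remain have no clear status, no scheduled postoperative AE follow-up and no place in the device-related AE rate

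*Protocol*

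**What the plan says.** **Who is a screen failure.** Protocol 6.1.2 gives a two-part definition: "Subjects who provide consent for participation but do not meet all of the study eligibility criteria and do not receive the study device". Protocol 6.3.1 uses one condition: "Subjects who are screened but do not have the study device placed should be considered screen failures".

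**When their data stop.** Protocol 6.1.3 states "Final eligibility will be determined intraoperatively" and "Data are to be collected for screen failure subjects from the time the ICF is signed until the subject is deemed a failure". For the AE eCRF it sets this limit on the operative period: "Any adverse event that occurs from the beginning of the surgical procedure until the subject is determined as screen failure will be recorded". Protocol 6.3.1 has screen failures with a protocol-defined AE followed until it resolves or stabilises. For a failed repair, the reason "as well as all information outlined in Section 6.2.2 must be recorded in the source documentation".

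**Who is followed.** Protocol 6.3.2 applies the visit schedule to successfully implanted subjects. Protocol 6.5 defines early termination, with its visit, as discontinuation after a successful implant.

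**General AE rules.** Protocol 8 runs AE collection from enrolment to study completion or early discontinuation. SAP 7.9 repeats this but inserts screen failure as a further end. Protocol 8.5 requires investigator-judged device-related AEs and all SAEs to be reported within 24 hours of awareness, and protocol 15 repeats the duty without the time limit.

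**Attempted implantation.** Protocol 9 includes, among devices to be recorded if they fail to meet specification, "devices with which implantation was attempted, but the device did not remain (was not used) in the subject".

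**Analysis.** The device-related AE rate (SAP 5.4) uses the mITT set, which is subjects implanted with the mesh (SAP 3). AEs of non-implanted subjects are summarised separately, and "their outcome data will not be collected or analyzed" (SAP 7.9; protocol 7.3 agrees).

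**The concern.** The objective includes device safety and performance. A subject whose mesh was handled, positioned and then taken out has been exposed to the device and to the operation. Device or handling problems could plausibly concentrate in this group. The protocol anticipates the group in Section 9, but its recording and follow-up rules are written for two others: subjects found ineligible and subjects successfully implanted.

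At stake is whether a complication that first appears after such an operation is looked for and recorded, and whether it can reach any reported rate. The separate AE table for non-implanted subjects can show only what the sites were told to record.

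**Working it through.** The point rests on text. The plan has no figure to reproduce, and the sample size of 120 has no stated statistical basis. The check follows one case: a consented subject, mesh attempted and not retained, with a new AE some days after surgery.

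1. **Status.** Under 6.3.1 the device was arguably not placed, so the subject is a screen failure. Under 6.1.2 a screen failure must also fail eligibility, which this subject may not have done. The heading of 6.3.1 names surgical repair failures as well, but gives them no status of their own. The classification is open, and two sites could code the same case differently.

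2. **If a screen failure.** By 6.1.3 the AE eCRF window runs from the start of surgery to the screen-failure decision, which for this subject is made during the operation. SAP 7.9 agrees, but protocol 8 does not list screen failure as an end. The duty in 6.3.1 to follow an AE to resolution sets no visit or period in which to find a new one.

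3. **If not a screen failure.** The subject is still not successfully implanted, so 6.3.2 gives no visit schedule and 6.5 gives no early termination visit. Section 8 would leave AE recording open, but no contact is planned at which to ask. An implanted subject has a first visit at day 30 ± 7, that is day 23 to 37.

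4. **What is still captured, by type of event.**
   - AE that began before the decision: recorded (6.1.3) and followed (6.3.1).
   - New SAE: reportable once known (8.5, 15), with no implant condition.
   - New non-serious AE judged device-related: also reportable once known.
   - New non-serious AE not judged device-related, such as a minor haematoma attributed to the procedure: outside the 24-hour duty. On the screen-failure reading it is also outside the AE eCRF window.
   - Device that failed its specification: the Device Failure eCRF applies (9), but that form concerns the device and not later patient harm.

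5. **Analysis.** A device-related AE in this subject, even if reported, is not in the SAP 5.4 rate, because mITT requires that the mesh has been implanted.

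6. **Size.** The documents give neither the number of such subjects nor their AE rate. With assumed counts, take 6 device-related events in 120 implanted subjects, 6/120 = 5.0%, and add 3 attempted-not-retained subjects:
   - none with an event: 6/123 = 4.9%
   - one: 7/123 = 5.7%
   - all three: 9/123 = 7.3%

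   The rate can move either way, so these figures show only that size and direction depend on what is assumed.

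7. **Cross-reference.** Section 6.3.1 points to 6.2.2 for what to record about a failed repair. Section 6.2.2 covers cultures when mesh is removed and infection is suspected. Surgical details are in 6.2.3.

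**The case against.** The strongest reply is that the 6.1.3 rule was not written for these subjects. It sits in text about subjects who fail eligibility, and footnote 1 of the Table of Study Events places the final eligibility check before device placement. In the planned sequence, the decision that closes the AE window therefore precedes any device contact. This stands as far as it goes: 6.1.3 is mainly about subjects never exposed to the mesh, and a reader who infers that attempted-not-retained subjects simply are screen failures goes beyond the documents. It does not close the gap, because the other reading leaves the same subjects without visits.

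The second reply is that reporting continues. Sections 8.5 and 15 have no implant condition, Section 8.5 asks for the eCRF whenever an AE occurs, and Section 8 records AEs from surgery onward. This also stands. A reader might infer that postoperative harms in this group are never collected or have nowhere to be recorded. The documents do not support that for serious or device-related events. These duties are, however, passive: they depend on the site learning of the event and, for non-serious events, on its causality judgement.

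Third, limiting rates to implanted subjects is a declared choice in a descriptive post-market study, and separate AE tabulation of the others is already planned. That justifies keeping mITT for the main analyses. It does not settle which AEs reach the separate table.

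**Conclusion.** The plan recognises subjects with attempted but not retained mesh and does not say what they are. On either available reading no study contact is scheduled to detect their postoperative AEs. On the screen-failure reading, protocol 6.1.3 and SAP 7.9 close the AE record for new-onset events at the intraoperative decision, in conflict with protocol 8. New non-serious AEs not judged device-related are therefore not systematically collected. Device-related AEs are reportable when known but do not enter the SAP 5.4 rate.

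It is tempting to conclude that the planned device-related AE rate will be too low. The documents do not show this: they give no count and no event rate for the group, and the assumed figures move in both directions. The conclusion rests on two assumptions: that at least one such subject occurs, which Section 9 treats as possible, and that a mesh tried and taken out does not count as implanted for mITT.

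**What to change.** - **Protocol 6.1.2, 6.1.3 and 6.3.1:** separate screen failures with no device contact from subjects with attempted but not retained mesh, using one definition throughout.
- **AE window for the second group:** record AEs through day 45, matching the primary endpoint period, from routine postoperative care records or by telephone. Another period could be defended, but one must be stated.
- **Reconcile** protocol 6.1.3, 6.3.1, 8 and 8.5 with SAP 7.9 on when AE collection ends for each group.
- **SAP 5.4 and 7.9:** add a supplementary tabulation of device-related AEs over all subjects with attempted implantation. Keep mITT for the primary endpoint and the main analyses.
- **Editorial:** check the reference to 6.2.2 in 6.3.1 against 6.2.3.

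The cost is short wording changes in both documents, a little extra AE data on what are likely to be few, already consented subjects, and one more table. The supplementary rate may come out slightly less favourable than the mITT rate. No clinical procedure changes.
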